2.8.1.1 Adverse events of special interest / grouping of AEs

Not Applicable

2.8.2 Deaths

The number and percentage of patients who died within 30 days of the last dose will be and all deaths (during the on-treatment and extended safety follow-up period) summarized with cause of deaths. Additional summary will be displayed to report all deaths up to 150 days

after last administration of study drug.

If study indication is primary reason for death (and not coded accordingly in the database) it must be included in the summary table. A patient listing of all deaths with recorded principal cause of death (if available) will also be provided, deaths during the extended safety follow-up period will be flagged.

2.8.3 Laboratory data

All laboratory values will be converted into SI units and the severity grade will be calculated using appropriate common terminology criteria (CTCAE v4.03).

A severity grade of 0 will be assigned when the value is within normal limits. For lab parameters for which severity grades are determined both through normal limits and absolute cut-offs, in the unlikely case when a local laboratory normal range overlaps into the higher (i.e. non-zero) CTCAE grade, the laboratory value will still be taken as within normal limits and assigned a CTCAE grade of zero.

The results will be listed separately for hematology and biochemistry laboratory tests, along with details on the CTCAE grades and/or classifications relative to laboratory normal ranges.

The results will be summarized separately for hematology and biochemistry laboratory tests as mentioned below:

1. Shift table from baseline to worst value on-treatment value, for those lab tests having CTCAE grades (frequency count and percentages)
2. Shift table from baseline to worst on-treatment value, for those lab tests not having CTCAE grades, based on the low/normal/high classification (frequency count and percentages)
3. Table for newly occurring on-treatment grades 3 or 4 (frequency count and percentages)

All laboratory assessments (including hematology/biochemistry/coagulation without CTC grades, urinalysis, thyroid function, cytokines, pregnancy, and virology) will be listed and those collected outside the on-treatment period will be flagged in the listings.

2.8.3.1 Liver function parameters

Liver function parameters of interest are total bilirubin (TBL), Alanine aminotransferase (ALT), Aspartate aminotransferase (AST).

The number (%) of subjects with worst post-baseline values will be summarized for the following:

1. ALT or AST > 3xULN
2. ALT or AST > 5xULN
3. ALT or AST > 8xULN
4. ALT or AST > 10xULN
5. ALT or AST > 20xULN
6. TBIL > 2xULN
7. TBIL > 3xULN

8. ALP>1.5xULN
9. ALP>2.0xULN
10. Hy's Law:ALT or AST > 3xULN & TBIL > 2xULN & ALP<2xULN

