5.4 Exclusion criteria

Patients eligible for this study must not meet **any** of the following criteria:

1. Presence of symptomatic CNS metastases, or CNS metastases that require local CNS-directed therapy (such as radiotherapy or surgery), or increasing doses of corticosteroids within the prior 2 weeks. Patients with treated brain metastases should be neurologically stable (for 4 weeks post-treatment and prior to study enrollment) and off steroids for at least 2 weeks before administration of any study drug.
2. History of severe hypersensitivity reactions to other mAbs
3. Patient with out of range laboratory values:
 - a. Creatinine clearance (calculated using Cockcroft-Gault formula, or measured) < 40 mL/min
 - b. Total bilirubin $> 1.5 \times$ ULN, except for patients with Gilbert's syndrome who are excluded if total bilirubin $> 3.0 \times$ ULN or direct bilirubin $> 1.5 \times$ ULN
 - c. Alanine aminotransferase (ALT) $> 3 \times$ ULN, except for patients that have tumor involvement of the liver, who are excluded if ALT $> 5 \times$ ULN
 - d. Aspartate aminotransferase (AST) $> 3 \times$ ULN, except for patients that have tumor involvement of the liver, who are excluded if AST $> 5 \times$ ULN

- e. Absolute neutrophil count (ANC) $< 1.0 \times 10^9/L$
- f. Platelet count $< 75 \times 10^9/L$
- g. Hemoglobin $< 9 \text{ g/dL}$
4. Impaired cardiac function or clinically significant cardiac disease, including any of the following:
 - a. Clinically significant and/or uncontrolled heart disease such as congestive heart failure requiring treatment (NYHA Grade ≥ 2), uncontrolled hypertension or clinically significant arrhythmia
 - b. QTcF $> 470 \text{ msec}$ on screening/baseline ECG or congenital long QT syndrome
 - c. Acute myocardial infarction or unstable angina pectoris < 3 months prior to study entry
5. Active, known or suspected autoimmune disease or a documented history of autoimmune disease within three years prior to screening with exception of:
 - a. Patients with vitiligo, type I diabetes mellitus, residual hypothyroidism due to an autoimmune condition only requiring hormone replacement, psoriasis not requiring systemic treatment, or conditions not expected to recur in the absence of an external trigger are permitted to enroll.
6. If otherwise eligible for the IO sub-group, patients previously exposed to anti-PD-1/PD-L1 treatment who are adequately treated for skin rash or with replacement therapy for endocrinopathies should not be excluded

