6.3.2.1 Follow up on potential drug-induced liver injury (DILI) cases

Patients with transaminase increase combined with TBIL increase may be indicative of potential DILI, and should be considered as clinically important events.

The threshold for potential DILI may depend on the patient's baseline AST/ALT and TBIL value; patients meeting any of the following criteria will require further follow-up as outlined below:

- For patients with normal ALT and AST and TBIL value at baseline: AST or ALT $> 3.0 \times$ ULN combined with TBIL $> 2.0 \times$ ULN
- For patients with elevated AST or ALT or TBIL value at baseline: [AST or ALT $> 2 \times$ baseline AND $> 3.0 \times$ ULN] OR [AST or ALT $> 8.0 \times$ ULN], combined with [TBIL $> 2 \times$ baseline AND $> 2.0 \times$ ULN]

Medical review needs to ensure that liver test elevations are not caused by cholestasis, defined as ALP elevation $> 2.0 \times$ ULN with R value < 2 in patients without bone metastases, or elevation of ALP liver fraction in patients with bone metastases.

Note: (The R value is calculated by dividing the ALT by the ALP, using multiples of the ULN for both values. It denotes whether the relative pattern of ALT and/or ALP elevation is due to cholestatic (R ≤ 2), hepatocellular (R ≥ 5), or mixed (R > 2 and < 5) liver injury).

In the absence of cholestasis, these patients should be immediately discontinued from study drug treatment, and repeat LFT testing as soon as possible, preferably within 48 hours from the awareness of the abnormal results. The evaluation should include laboratory tests, detailed history, physical assessment and the possibility of liver metastasis or new liver lesions, obstructions/compressions, etc.

1. Laboratory tests should include ALT, AST, albumin, creatine kinase, total bilirubin, direct and indirect bilirubin, GGT, prothrombin time (PT)/INR and alkaline phosphatase.
2. A detailed history, including relevant information, such as review of ethanol, concomitant medications, herbal remedies, supplement consumption, history of any pre-existing liver conditions or risk factors, should be collected.
3. Further testing for acute hepatitis A, B, C or E infection and liver imaging (e.g. biliary tract) may be warranted.
4. Additional testing for other hepatotropic viral infection (CMV, EBV or HSV), autoimmune hepatitis or liver biopsy may be considered as clinically indicated or after consultation with specialist/hepatologist.

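### The SAP's Hy's Law row has no concurrency condition and does not match the protocol's own liver-injury criteria, so it can miscount in both directions

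*SAP*

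**What the plan says.** SAP 2.8.3.1 lists ten liver rows under one lead-in: "The number (%) of subjects with worst post-baseline values will be summarized for the following". Rows 1 to 9 each use one threshold (ALT or AST, bilirubin, or ALP). Row 10 is the only one that combines parameters: "Hy's Law:ALT or AST > 3xULN & TBIL > 2xULN & ALP<2xULN". The section does not say whether the three values must share a sample or fall within a time window. It does not mention baseline status, the R value, bone metastases or protocol 6.3.2.1.

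Protocol 6.3.2.1 defines potential drug-induced liver injury differently:

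- **Baseline.** "The threshold for potential DILI may depend on the patient's baseline AST/ALT and TBIL value". With normal baseline values the rule is AST or ALT above 3xULN with bilirubin above 2xULN. A second rule applies as follows: "For patients with elevated AST or ALT or TBIL value at baseline". It requires AST or ALT either above both 2x baseline and 3xULN, or above 8xULN. It also requires bilirubin above both 2x baseline and 2xULN.
- **Cholestasis.** Without bone metastases, this means ALP above 2xULN together with R below 2, where R is ALT divided by ALP in multiples of ULN. The alternative is "elevation of ALP liver fraction in patients with bone metastases".
- **Reporting.** Cases confirmed on repeat testing, with no other cause found, are reported as SAEs.

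Protocol 5.4 caps entry ALT and AST at 3xULN, "except for patients that have tumor involvement of the liver", for whom the cap is 5xULN. Total bilirubin may be up to 1.5xULN, or 3xULN in Gilbert's syndrome. Protocol Table 4-1 includes a castration-resistant prostate cancer cohort. SAP section 4 declares changes to the full analysis set and safety set only.

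**The concern.** Taking worst post-baseline values is harmless for a one-parameter row. For a composite it is not, because the worst values of three parameters can come from three different dates. The direction of the ALP condition makes this worse. Applied to the worst ALP, it requires that ALP never reached 2xULN in the whole observation period.

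Row 10 is the only planned summary that combines transaminases with bilirubin. The treatment is a dual checkpoint blockade. Grade 4 autoimmune hepatitis is among the dose-limiting toxicities already reported with it (protocol 1.2.3.2), and hepatitis is named as a combination risk (protocol 2.6). There is no data monitoring committee (protocol 8.6), and the SAP has no grouping of adverse events of special interest (SAP 2.8.1.1). A reader of the study report would take row 10 as the laboratory count of serious liver injury. That reader would be unable to reconcile it with SAEs reported under a different definition.

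**Working it through.** The documents give no expected count, so there is no figure to reproduce. The check applies three rules to constructed patients. All values are multiples of ULN.

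**Rules**

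1. *Row 10, literal:* max(ALT/AST) > 3, max(TBIL) > 2 and max(ALP) < 2, each maximum taken over all post-baseline visits.
2. *Row 10, same visit:* at least one visit with ALT/AST > 3, TBIL > 2 and ALP < 2 together.
3. *Protocol 6.3.2.1, visit by visit:* the baseline-dependent thresholds, less cholestasis (ALP > 2 with R < 2 or, with bone metastases, a raised ALP liver fraction). The repeat-testing and alternative-cause steps are left out because they are not laboratory thresholds.

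Patients A, B, C, F and G have normal baseline values (ALT 0.8, TBIL 0.8).

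| Patient | Values (ALT / TBIL / ALP) | Literal | Same visit | Protocol |
|---|---|---|---|---|
| A: peaks at different times | 4 / 0.8 / 1.2, later 1 / 2.5 / 1.2 | counted | no | no |
| B: later ALP rise | 6 / 3 / 1.5, later 1 / 1 / 2.5 | no | counted | case |
| C: raised ALP, high R | 10 / 3 / 2.5 | no | no | case |
| D: liver involvement, baseline ALT 4, TBIL 1.2 | 4 / 2.2 / 1.5 | counted | counted | no |
| E: liver involvement and Gilbert's, baseline ALT 4, TBIL 2.5 | 4 / 2.5 / 1.5 | counted | counted | no |
| F: bone metastases, ALP not of liver origin | 6 / 3 / 4 | no | no | case |
| G: concurrent, no complication | 6 / 3 / 1.5 | counted | counted | case |

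**Reasoning for each disagreement**

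- **A.** The maxima are 4, 2.5 and 1.2, so the literal rule is met, but no single visit meets it.
- **B.** The first visit meets the protocol rule. The later ALP makes max(ALP) = 2.5, which is not below 2, so the literal rule removes the patient.
- **C.** R = 10 / 2.5 = 4. This is not below 2, so the protocol does not call it cholestasis. Row 10 excludes it because ALP is 2.5.
- **D.** Twice baseline ALT is 2 x 4 = 8. A value of 4 is neither above that nor above 8xULN, so the protocol rule fails. Row 10 ignores baseline.
- **E.** The ALT test fails as in D (4 is not above 8), and TBIL fails as well (2.5 is not above 2 x 2.5 = 5). Nothing has changed since entry and the baseline values are within the ALT and total-bilirubin limits, yet row 10 counts the patient.
- **F.** Total ALP of 4 removes the patient from row 10. The protocol looks at the liver fraction, taken here as not raised, and keeps the case. (R = 6 / 4 = 1.5 is not used with bone metastases.)

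**Result.** The literal rule gives three false counts (A, D, E) and three missed cases (B, C, F). Same-visit evaluation corrects A and B. C, D, E and F stay wrong until the protocol's baseline and cholestasis rules are also applied. The patients were chosen to show the mechanisms, so these counts are not estimates of frequency.

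**The case against.** Several points can fairly be made against this.

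- **The algorithm is not spelled out.** One generic lead-in covers nine simple rows and one composite, and a programmer could evaluate row 10 by visit. This stands, so errors can occur but are not certain. It does not help C, D, E or F.
- **The protocol sets no time window either.** Section 6.3.2.1 joins the two elevations without saying how close in time they must be. This also stands. Patient A is a non-case under a visit-by-visit reading, and any window has to be chosen.
- **Would a later ALP exist?** In the absence of cholestasis, 6.3.2.1 takes such a patient off study drug at once, so an example with the ALP rise several treatment cycles later would not fit. But 6.3.2.1 also calls for prompt repeat tests that include ALP, and 6.3.2 requires weekly and then roughly four-weekly follow-up. Later samples should therefore exist, although the SAP does not say how far post-baseline runs for this row.
- **The purposes differ.** The protocol text is a follow-up and SAE-reporting pathway, and protocol 10.5.2.1.2 specifies no liver-injury table. So the SAP does not breach a protocol-specified analysis. It still presents a second, unexplained definition of much the same event.
- **Cases are captured elsewhere.** Confirmed cases are reported as SAEs, which are tabulated and listed (SAP 2.8.1), and biochemistry results are listed (SAP 2.8.3). This limits the damage to one row.
- **Liver fraction is not routine.** Protocol Table 7-3 lists only alkaline phosphatase, so that part of the definition cannot be assumed programmable.

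**Conclusion.** The point holds in a limited form. As written, row 10 can misclassify in both directions because it has no concurrency condition. On the kinder same-visit reading it still conflicts with protocol 6.3.2.1 on raised baseline, on R value when ALP is high, and on bone metastases. SAP section 4 does not explain the difference. How many patients would be affected cannot be derived from the documents. The change is worth making, but no stopping or interim rule depends on this row.

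Three stronger readings are not supported:

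- A reader might infer that true cases *are* missed and false ones *are* counted. The SAP does not fix the algorithm, so only *can be* is justified.
- A reader might infer that liver-injury cases disappear from the safety report. SAE reporting and the laboratory listings contradict that.
- A reader might infer that the single-parameter rows also need rebuilding, because a patient entering at ALT 4xULN falls in the above-3xULN row unchanged. SAP 2.8.3 already plans shift tables from baseline to worst value and a table of newly occurring grade 3 or 4 values, which largely answer this.

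The conclusion assumes that 6.3.2.1 is the intended reference for liver injury in this trial.

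**What to change.** In SAP 2.8.3.1:

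1. Derive row 10 from concurrent ALT/AST, TBIL and ALP, meaning the same sample or a stated short window. State the observation period that applies.
2. Add a count and a patient listing on the laboratory criteria of protocol 6.3.2.1: baseline-dependent thresholds, with cholestasis as ALP above 2xULN and R below 2. Flag patients with bone metastases for medical review, using the ALP liver fraction only where it was measured.
3. If the sponsor prefers to keep only the simple Hy's Law definition, state and justify the departure in SAP section 4.

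ALT, AST, TBIL and ALP belong to one chemistry panel (protocol Table 7-3), so no new data collection is needed. The cost is SAP wording and modest programming. Only the analysis definition changes. No clinical rule is altered.

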2.8.4 Other safety data

Other safety data (ECG, vital signs, ECOG performance status, chest X-ray) will be listed.

2.8.4.1 ECG and cardiac imaging data

A standard 12-lead ECGs including PR, QRS, QT, QTcF, QTcB, and HR intervals will be obtained for each subject during the study. The ECGs on C1D1, C2D1, C3D1, C4D1, C5D1 and C6D1 must be performed in triplicate.

The number and percentage of patients with notable ECG values will be presented. The denominator to calculate percentages for each category is the number of patients with both a baseline and a post-baseline evaluation. A newly occurring post-baseline ECG notable value is defined as a post-baseline value that meets the criterion at post-baseline but did not meet the criterion at baseline.

Notable ECG values are defined as:

QT and QTcF

1. New value of > 450 and ≤ 480 ms
2. New value of > 480 and ≤ 500 ms
3. New value of > 500 ms
4. Increase from baseline of > 30 ms to ≤ 60 ms
5. Increase from baseline of > 60 ms

HR

6. Increase from baseline > 25 % and to a value > 100 bpm
7. Decrease from baseline > 25 % and to a value < 50 bpm

PR

8. Increase from baseline > 25 % and to a value > 200 ms
9. New value of > 200 ms
10. QRS Increase from baseline > 25 % and to a value > 120 ms
11. New values of QRS > 120 ms

All ECG measurements will be listed and those collected outside the on-treatment period will be flagged in the listings. Notable values will be flagged in the listings. Qualitative ECG findings will be listed as well.

2.8.4.2 Vital signs

The number and percentage of patients with notable vital sign values (high/low/high and low) will be presented. The denominator to calculate percentages for each category is the number of patients with both a baseline and a post-baseline evaluation.

Notable vital sign values are defined as:

Systolic blood pressure

1. High: ≥ 180 mmHg with increase from baseline of ≥ 20 mmHg
2. Low: ≤ 90 mmHg with decrease from baseline of ≥ 20 mmHg

Diastolic blood pressure

3. High: ≥ 105 mmHg with increase from baseline of ≥ 15 mmHg
4. Low: ≤ 50 mmHg with decrease from baseline of ≥ 15 mmHg

Pulse rate

5. High: ≥ 100 bpm with increase from baseline of ≥ 25 bpm
6. Low: ≤ 50 bpm with decrease from baseline of ≥ 25 bpm

Weight

7. High: Increase from baseline of ≥ 10 %
8. Low: Decrease from baseline of ≥ 10 %

Body temperature

9. High: ≥ 39.0 °C
10. Low: ≤ 35.0 °C

All vital sign values will be listed and those collected outside the on-treatment period will be flagged in the listings. Notable values will be flagged in the listings.

2.8.4.3 ECOG performance status

ECOG performance status will be summarized and listed by visit based safety set.

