10.5.2.1.3 Other safety data

Summary statistics for data from other tests will be provided, notable values will be flagged, and any other information collected will be listed as appropriate.

Descriptive summary statistics will be provided for :

- Electrocardiograms: changes from baseline to last available ECG results
- Cardiac imaging: number and percentage of patients with notable LVEF values
- Vital signs: number and percentage of patients with at least one post-baseline vital sign abnormality
- ECOG performance status: shift table comparing baseline to worst post baseline ECOG performance status.
- All other safety related procedures as required
- Listings with flagged notable values and any other information collected will be provided as appropriate.

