5.1.2	AE and ConMeds date imputation	32
5.2	AEs coding/grading	34
5.3	Laboratory parameters derivations	34
5.4	Statistical models	34
5.4.1	Primary analysis	34
5.4.2	Secondary analysis	35
6	Reference	35

List of abbreviations

AE	Adverse event
ATC	Anatomical Therapeutic Classification
AUC	Area Under the Curve
bid	bis in diem/twice a day
CSR	Clinical Study report
CTC	Common Toxicity Criteria
CTCAE	Common Terminology Criteria for Adverse Events
DMC	Data Monitoring Committee
FAS	Full Analysis Set
eCRF	Electronic Case Report Form
IVR	Interactive Voice Response
IWR	Interactive Web Response
MedDRA	Medical Dictionary for Drug Regulatory Affairs
NCI	National Cancer Institute
o.d.	Once Daily
OS	Overall Survival
PFS	Progression-Free Survival
PK	Pharmacokinetics
PPS	Per-Protocol Set
PRO	Patient-reported Outcomes
qd	Qua'que di'e / once a day
QoL	Quality of Life
RAP	Report and Analysis Process
RECIST	Response Evaluation Criteria in Solid Tumors
SAP	Statistical Analysis Plan
SOC	System Organ Class
TFLs	Tables, Figures, Listings
WHO	World Health Organization

1 Introduction

This statistical analysis plan (SAP) describes detailed statistical methodology for the analysis of data from study CPDR001XUS01. Study treatment under evaluation in this study are PDR001 and LAG525.

The primary efficacy variable, clinical benefit rate, will be analyzed by a Novartis designated Contract Research Organization (CRO), [REDACTED]. Analysis details are provided in Appendix 4 of the protocol, which is also included in Section 2.5 of this Statistical Analysis Plan.

All other data will be analyzed by Novartis or designated CRO, according to Section 10 of the study protocol which will be available in Appendix 16.1.1 of the Clinical Study Report(CSR). Important information is given in the following sections and details will be provided, as applicable, in Appendix 16.1.9 of the CSR. All statistical analyses will be performed using SAS® Version 9.4 (or higher).

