2.1 Data analysis general information

Data from all centers that participate in this protocol will be used. Data used for the analyses specified in this document will come from the Electronic Data Capture (EDC) system. The analyses stated in this document will be based on all patients' data up to the time when all enrolled patients have either discontinued or completed 2 years of study therapy and 150 days of safety follow up.

All statistical analyses presented in this document are related to patient background information, efficacy, and safety. All analyses are descriptive and no hypothesis testing is planned (except for the primary efficacy variable, which is described in [Section 2.5](#) below). For continuous data, the number of observations, mean, standard deviation (SD), median, 25th and 75th percentiles,

minimum, and maximum will be presented. For categorical data, frequencies and percentages will be presented.

In general, data from all centers will be combined for any analysis. There will be no stratification factor considered for the analysis with the exception of tumor type in the primary efficacy variable analyses. Missing data will not be imputed. All data collected in the study will be presented in the listings.

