2.14 Interim analysis

Scheduled interim data reviews will occur for the primary endpoint of clinical benefit rate only as required by the Bayesian Hierarchical design. The first interim data review will be performed after the 5 subjects have CBR data available within a cohort. Interim analyses will continue every 3 months thereafter provided at least 10 subjects contribute new CBR data to the subsequent interim. At each interim analysis, the tumor cohorts will be evaluated for early futility and early success by comparing posterior quantities for the response rate to pre-specified early stopping criteria.

There is no plan for a formal interim analysis of safety or other secondary endpoints for this study. However, for publication or other purposes, interim data review of clean data will be performed as necessary. At these interim reviews, patient demographics/baseline characteristics, the primary and secondary endpoints as applicable, and all important safety endpoints will be summarized. No formal report will be issued for these data reviews.

3 Sample size calculation

The sample size was chosen by the usual criteria of obtaining adequate power for the alternative hypothesis of interest as given in Sections 6.2.2 and 6.2.3 of Appendix 4 of protocol. This hypothesis corresponds to a generally effective treatment across cohorts and incorporates variation in treatment effects to reflect the realistic expectation that treatment effects may differ by cohort. In this setting, analytical power calculations are not possible, but the design was simulated to obtain the power of the study as shown in the appendix. The sample sizes shown (minimum of 5 for futility stopping, minimum of 10 for early success and maximum of 24 as a cohort cap) achieve adequate power for the alternative hypothesis. The simulations included the expected variable accrual by simulating a Poisson process with expected accrual also shown in the appendix.

4 Change to protocol specified analyses

As per study team suggestion, the definitions of full analysis set (FAS) and safety set have been changed(defined in [section 2.2](#)).

5 Appendix

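### The SAP omits the protocol's baseline-to-worst ECOG shift table and gives only a by-visit summary, which can make performance status look more stable than it is; the change is not declared

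*SAP*

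**What the plan says.** Protocol 10.5.2.1.3 (Other safety data) names the analysis: "ECOG performance status: shift table comparing baseline to worst post baseline ECOG performance status". Each assessed patient is counted once, at the worst value, against their own starting point.

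SAP 2.8.4.3 is the only place where the SAP defines a post-baseline ECOG analysis: "ECOG performance status will be summarized and listed by visit based safety set". Its parent section, 2.8.4, goes no further than a listing: "Other safety data (ECG, vital signs, ECOG performance status, chest X-ray) will be listed". Neither mentions a shift table or a worst value.

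The SAP does use that format for laboratory data in 2.8.3: "Shift table from baseline to worst value on-treatment value, for those lab tests having CTCAE grades". For ECG and vital signs it counts patients with notable values among those with both a baseline and a later evaluation.

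SAP section 4, which records departures from the protocol, has one entry: "As per study team suggestion, the definitions of full analysis set (FAS) and safety set have been changed". The document history at the front of the SAP does not mention ECOG either. SAP section 1, however, says that data other than the primary variable are analysed "according to Section 10 of the study protocol which will be available in Appendix 16.1.1" of the clinical study report, and protocol Section 10 contains the shift table.

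**The concern.** The two tables answer different questions. The shift table shows how many patients got worse and by how much. A by-visit table shows the distribution of ECOG among those with a value at that visit. SAP 2.1 states: "Missing data will not be imputed". A patient who has left therefore contributes nothing to later columns.

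Leaving is not random here. Treatment ordinarily ends at progression (protocol 4.1, SAP 1.1.1). Protocol 7.1.4 moves patients with unconfirmed progression and clinical deterioration or toxicity into safety follow-up. Entry requires ECOG 0 or 1 (protocol 5.3), so worsening is what a safety reader looks for, and the patients who worsen are the likelier ones to disappear from later columns.

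At stake is the reading of one safety output. A clinical study report built from SAP 2.8.4.3 would not show the number of patients who declined from baseline, and its visit trend could understate decline.

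**Working it through.** **1. Text comparison.** This carries the point and needs no model.

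| Item | Protocol 10.5.2.1.3 | SAP 2.8.4.3 |
|---|---|---|
| Unit | Patient, once | Patient-visit |
| Value used | Worst post-baseline | Value at each visit |
| Paired with own baseline | Yes | No |
| Who is included | Every patient with a post-baseline value | Those assessed at that visit |

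The visit distributions cannot be turned into the shift table, because they do not link a patient's values across visits.

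**2. Possible attrition under the plan's own figures.** Inputs are the median PFS values in protocol Table 10-1 (also Table 1 of Appendix 4), with the exponential assumption of Appendix 4 section 6.1.2. The formula is S(t) = 0.5^(t / median), t in months. At t = 6 it reproduces the plan's historical rates, for example SCLC 0.5^(6/1.5) = 6.25%. At 30.4375 days per month, week 12 is 84/30.4375 = 2.76 months and week 24 is 168/30.4375 = 5.52 months.

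| Group | Median (mo) | Plan's rate | S(6 mo) | S(week 12) | S(week 24) |
|---|---|---|---|---|---|
| SCLC | 1.5 | 6.25% | 6.25% | 27.9% | 7.80% |
| Ovarian, DLBCL | 3 | 25.00% | 25.00% | 52.9% | 27.94% |
| Prostate | 4 | 35.40% | 35.36% | 62.0% | 38.43% |
| Gastroesophageal, NET | 5 | 43.50% | 43.53% | 68.2% | 46.53% |
| Sarcoma | 6.2 | 51.10% | 51.13% | 73.5% | 53.95% |

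These are progression-free shares at historical rates. They illustrate how heavy attrition could be; they do not estimate attendance.

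**3. What selective drop-out does to each table.** This is an illustration. The documents give no ECOG transition or drop-out rates, so every rate is an assumption. It runs eight 3-week cycles with entry at ECOG 0 (40%) or 1 (60%), improvement of 2% per cycle and drop-out of 10% per cycle below ECOG 2. Worsening and drop-out at ECOG 2 or more vary by row. All results are the percentage at ECOG 2 or more.

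| Worsening per cycle | Drop-out per cycle at ECOG ≥2 | By-visit, cycle 1 → 4 → 8 | Full cohort, cycle 8 | Worst value, EOT counted | Worst value, EOT not counted |
|---|---|---|---|---|---|
| 8% | 10% (unrelated) | 4.9 → 17.5 → 31.0 | 31.0 | 23.8 | 23.9 |
| 8% | 50% | 2.8 → 5.5 → 6.1 | 30.8 | 23.9 | 13.4 |
| 8% | 80% | 1.1 → 1.5 → 1.5 | 31.0 | 23.8 | 5.5 |
| 15% | 50% | 5.1 → 11.2 → 12.9 | 52.8 | 41.0 | 23.8 |
| 15% | 80% | 2.1 → 2.9 → 3.1 | 52.7 | 41.4 | 9.7 |

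Three results follow.

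- When drop-out is unrelated to ECOG, the by-visit share equals the full-cohort share, so there is no false stability.
- When drop-out tracks ECOG, the by-visit share lies far below the full-cohort share. It is nearly flat at 8% worsening.
- The shift table resists this selection only if the value at leaving is captured. Without EOT values it also falls, from about 24% to 13.4% or 5.5%.

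**The case against.** **The shift table is not expressly withdrawn.** SAP section 1 still refers to protocol Section 10, so replacement is inferred from omission. This stands as a matter of wording. It leaves two unreconciled texts, and someone programming from SAP 2.8.4.3 would not produce the table.

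**Leavers may be visible.** Protocol 7.1.5 requires an EOT visit, and Table 7-1 has an EOT column. If ECOG is taken there and tabulated as a visit, leavers appear in that column. This stands as an open question: protocol 7.2.2.4 defers the timing to Table 7-1, and the ECOG row is not in the text available for this review. Even so, an EOT column would not pair each patient's baseline with the worst value.

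**The attrition figures are not attendance.** This stands. Scheduled imaging starts at week 12, so undetected progression before then need not end attendance. Treatment beyond progression is allowed (protocol 7.1.4, 7.2.1.1), and the medians are historical control values. A reader might infer that a 24-patient SCLC cohort would have about two patients left at week 24 (24 × 7.8% = 1.9). The documents do not support that as a forecast. Passing 10 patients requires a posterior probability above 0.70 of beating the historical rate, and with no effect in any group SCLC expands in only 19.6% of simulated trials (Appendix 4, Table 6).

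**Nothing is lost.** All values are listed, frequencies accompany percentages (SAP 2.1), and discontinuations are tabulated by reason (SAP 2.3.1). A careful reader could see the shrinking counts. This limits the harm, but it still leaves the reader to work out from listings who worsened.

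**Conclusion.** The discrepancy is real and undeclared. The protocol commits to a baseline-to-worst ECOG shift table; the SAP specifies only a by-visit summary and listing, and section 4 is silent on the difference. The by-visit summary does not count patients who worsened from baseline, and it can make performance status look more stable than it is.

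A reader might go further and infer that ECOG will look stable or improving. The documents do not support that. No scenario in the illustration produced an improving trend, and drop-out unrelated to ECOG produced no distortion. The size depends on two things the documents do not settle: how strongly leaving tracks ECOG, and whether ECOG is tabulated at EOT.

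The consequence is confined to a descriptive safety output. The primary analysis and the interim decision rules are untouched. The change is still worth making, because it restores a protocol commitment at almost no cost.

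**What to change.** In SAP 2.8.4.3, restore the protocol's shift table of baseline to worst post-baseline ECOG, on the safety set and by tumor cohort. State that EOT and unscheduled values count where collected, and add a category for patients with no post-baseline value so that each row accounts for everyone. Check the ECOG row of protocol Table 7-1 to confirm whether EOT values exist.

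Keep the by-visit summary as a supplement, with n shown at each visit. Reducing it to a listing is unnecessary. If the team prefers the by-visit summary alone, record and justify that in SAP section 4.

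The cost is a sentence or two of SAP text and one extra standard table from data already collected.
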